### **Secondary Outcomes**

1. A change in the frequency of GI symptoms as assessed by the Gastrointestinal History questionnaire.

A secondary outcome of this study is the postulated improvement in the participant's GI symptom frequency scores over the 12 and 28-week treatment period. Assessing the severity of symptoms in children with ASD is difficult as many are non-verbal or unable to answer questions regarding symptoms. In 2003 the Childhood Autism Risks from Genetics and the Environment (CHARGE) study [70] developed and began using a frequency assessment of GI symptoms in children with ASD, which they called the Gastrointestinal History Questionnaire. The Gastrointestinal History questionnaire (GIH) includes 10 Likert scale items for the following symptoms: abdominal pain, gaseousness/bloating sensation, diarrhoea, constipation, pain on stooling, vomiting, sensitivity to foods, difficulty swallowing, blood in stools and blood in vomit. In addition, the GIH includes four yes/no questions asking about the presence of food allergies, diet restrictions, food dislikes, and whether any GI diagnosis has ever been given. Finally there are open-ended questions asking parents to list; food allergies, reasons for diet restrictions, and what GI condition has been diagnosed. For this study, the GIH will be used by the clinician as a pro forma for interview with patients and their parents.

- A change in Aberrant Behaviour Checklist (ABC) score
   A secondary outcome of this study is the postulated improvement in the participant's behavior.
   Maladaptive behavior will be measured using five subscales of the ABC: irritability (15 items),
   lethargy/social withdrawal (16 items), stereotypy (7 items), hyperactivity (16 items) and
   inappropriate speech (4 items) as validated by Kaat et al. [59].
   This one-page, parent completed assessment is the gold standard evaluation for the assessment
   of autism severity and can also be used for assessing response to treatment interventions in
   terms of behavior.
- A change in Autism Parenting Stress Index (APSI)
   A secondary outcome is a change in the baseline APSI score to the score after 12 weeks of
   treatment and after 28 weeks of treatment.

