## **Statistical analysis**

#### Summary of baseline data and flow of participants

As the study is a crossover study, each participant becomes their own control so there is not a need to compare characteristics between the two study arms. Baseline variables as follows will be collected and used in statistical analyses to see whether they are associated with treatment response:

Age ATEC score (done by parent) ATEC score (done by educator) ABC total score and subscale scores GIH frequency score Clinician's global assessment

We plan to produce a CONSORT flow diagram.

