#### Secondary outcome analysis

#### GIH

Analyse the frequency score after treatment with the active product compared to baseline and contrast that to the score after the placebo treatment. To report what proportion and number of participants showed a reduction in the frequency score after active treatment, what the mean reduction was with confidence interval.

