The efficacy of the multi-strain probiotic, Vivomixx, on behaviour and gastrointestinal symptoms in children with autism spectrum disorder (ASD)

NCT03369431

18th March 2021

Statistical Analysis Plan

Principal Analysis

The principal analysis will look for between phase differences in outcome measures assuming no order of treatment effects, which will be investigated in the secondary analysis. The outcome variables consider are:

1. Change from baseline ATEC scores (**Interval Data: between groups**): **PRIMARY OUTCOME MEASURE**

Secondary measures

1. Change from baseline ABC scores (**Interval Data: between groups**)
2. Gastrointestinal events: frequency of abdominal pain, gaseousness, diarrhoea, constipation, pain on stooling, and difficulty swallowing. (**Interval Data: between groups**)
3. Bristol Stool Scale: proportion of phase participants with type 4 stool samples after active treatment. (**Dichotomous data: between groups**)
4. Clinical Global Impression (**Interval Data: between groups**)
5. Treatment Effectiveness Score (**Interval Data: between groups**)
6. Correlations: ATEC vs constipation frequency on GI History; ATEC vs diarrhoea frequency on GI History; ATEC vs ATEC components (i.e. Health/Physical/Behaviour scores); ATEC vs Clinical Global Impression. (**Interval Data: Correlation**)

All between groups interval data will be subject to the following protocol for statistical analysis.

1. Calculation of mean, standard error and median and 25-75 quartiles for both phases.
2. Kolmogorov-Smirnov test to assess normality in the between phase differences in primary and secondary outcome measure with interval measurements.
3. If there is no statistically significant ($\alpha = 0.05$) evidence of non-normality in the mean differences then a paired t-test¹ will be used to assess statistical significance.
4. If there is statistically significant ($\alpha = 0.05$) evidence of non-normality in the mean differences, then a Wilcoxon-Signed-rank-test will be used to assess statistical significance.

All between groups dichotomous data will be assessed for statistical significance by calculating the Relative Risk and corresponding 95% confidence intervals for exposure to the active agent. Corresponding p-values can, if desired, be calculated from the 95% Confidence Intervals; however, 95% Confidence Intervals that do not contain the value 1 are statistically significant at $\alpha = 0.05$.

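### The SAP drops the protocol's GIH frequency score for six of its ten symptoms, with no reason given and no rule for what would count as a GI effect

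*SAP*

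**What the plan says.** **Protocol.** Under Secondary Outcomes, item 1 is change in GI symptom frequency on the GIH, which "includes 10 Likert scale items for the following symptoms". The ten are abdominal pain, gaseousness or bloating, diarrhoea, constipation and pain on stooling, followed by "vomiting, sensitivity to foods, difficulty swallowing, blood in stools and blood in vomit". The GIH analysis section then works with one score: "Analyse the frequency score after treatment with the active product compared to baseline and contrast that to the score after the placebo treatment". It also promises the proportion of children who improve on active treatment, and the mean reduction with a confidence interval. The baseline section likewise lists a single "GIH frequency score" among the candidate predictors of response. No section says how the score is built, and Secondary Outcomes once uses the plural, scores.

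**SAP.** Principal Analysis, secondary measure 2, is labelled gastrointestinal events, classed as interval data, and consists of the "frequency of abdominal pain, gaseousness, diarrhoea, constipation, pain on stooling, and difficulty swallowing". No GIH total appears. The SAP then states: "All between groups interval data will be subject to the following protocol for statistical analysis". That procedure is phase summaries, a Kolmogorov-Smirnov check, and a paired t-test or Wilcoxon signed-rank test. It includes no confidence interval for the difference, no multiplicity rule for the GI symptoms and no explanation of the item list.

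**The concern.** GI change is the first secondary objective in the protocol, part of the question in the Protocol Summary and part of the SAP's own title. A reader of the results will want to know whether GI symptoms improved. Under the protocol one score answers that. Under the SAP there are six candidate answers and no statement of which one decides, or how many must be positive.

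The point is narrower than a general complaint about uncorrected secondary outcomes. An outcome that the protocol names in the singular has been replaced by an unexplained subset of its own items. Two things are at stake: an unstated false-positive rate for the GI conclusion, and a reported GI result that cannot be matched to the outcome in the protocol.

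**Working it through.** **Item count.** Set the protocol's ten GIH items against the SAP's six. Kept: abdominal pain, gaseousness, diarrhoea, constipation, pain on stooling, difficulty swallowing. Missing: vomiting, sensitivity to foods, blood in stools, blood in vomit. So 10 − 6 = 4 items are dropped.

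**Are the six tested separately?** The SAP does not say so in words. It defines no composite, and its correlation analyses use single GIH items (constipation frequency and diarrhoea frequency). Separate testing is therefore the natural reading, and the figures below depend on it.

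**Inputs.**
- Number of tests: 6 (SAP, secondary measure 2).
- Level per test: two-sided 0.05. This is inferred from the Protocol (Primary outcome analysis; Sample size calculation). For interval data the SAP attaches 0.05 only to the normality check; its other use is the confidence-interval rule for dichotomous data.
- Decision rule: any one significant symptom counts as a GI effect. Assumed, because the SAP gives no rule.
- Correlation between the within-child symptom differences: not in either document, so shown as a range.

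**The plan's own figure.** Neither document states a family-wise error rate for GI measures, so there is none to reproduce. The nearest stated figure is power in the Sample size calculation: 80% for a Wilcoxon test with 74 children and dz = 0.34. Using the Wilcoxon relative efficiency of 3/π, I obtain 80.5%, which agrees. It does not enter the error-rate calculation. The 74 is used only as the sample size in the simulation check.

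**At least one false positive, either direction, no true effect on any symptom.**
- Independent items: 1 − 0.95^6 = 1 − 0.7351 = 26.5%.
- Common correlation ρ: with c = 1.96 and U standard normal, the rate is 1 − E[{Φ((c − √ρ·U)/√(1 − ρ)) − Φ((−c − √ρ·U)/√(1 − ρ))}^6], integrated numerically over U.

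| Assumed correlation | Chance of at least one false positive |
|---|---|
| 0 | 26.5% |
| 0.3 | 24.1% |
| 0.5 | 20.7% |
| 0.7 | 16.4% |
| 0.9 | 10.8% |
| One score, one test | 5% |

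Simulated paired t-tests with 74 children give 27.0%, 24.5% and 20.7% at correlations 0, 0.3 and 0.5. For two-sided tests on jointly normal statistics the independent case is the upper limit whatever the correlations (Šidák's inequality), so about 26% is a ceiling.

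**False positives in favour of Vivomixx only.** Independent: 1 − 0.975^6 = 14.1%. At correlation 0.3 it is 12.2%, and at 0.5 it is 10.4%. One score: 2.5%. Some pairs, such as constipation and diarrhoea, could be negatively correlated. Even then the rate cannot exceed 6 × 2.5% = 15%.

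**With adjustment across the six.** Bonferroni at 0.05/6 = 0.0083 gives 1 − (1 − 0.0083)^6 = 4.9% if the items are independent.

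**The case against.** The case for leaving the SAP alone has several parts.

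- *The protocol's score is not well defined.* No scoring rule is given, the plural appears once, and the GIH analysis section names no test or significance level. This stands. The single score is a fair reading of two sections, and the 5% comparator assumes that it would be tested once at 0.05. The missing rule has to be part of the fix.
- *Six separate tests at 0.05 are an inference.* This also stands. A reader might infer that the SAP raises the false-claim rate to between 21% and 26% as a matter of fact. The documents do not support that. The level is unstated for these tests, the any-one-counts rule is assumed, and 21% is not a floor because no correlation is given.
- *The two-sided figure counts false worsening too.* Correct. For a claim that GI symptoms improved, 10% to 14% against 2.5% is the relevant comparison at correlations from 0.5 to 0.
- *The item choice may be sensible.* Five of the six kept items match GI symptoms in the Inclusion criteria, and none of the four dropped items is listed there. Difficulty swallowing does not fit this pattern, and the SAP offers no reason of its own.
- *The SAP was allowed to add detail.* Protocol, Sensitivity and other planned analyses, foresees a more detailed plan, revised on blind review and finalised before the blind is broken. A reader might infer that items were picked after results were seen. Nothing in the documents shows that. The gap is one of explanation.
- *A total score has weaknesses.* It adds constipation to diarrhoea, which can move in opposite directions. This is a genuine cost. It argues for showing the symptoms descriptively beside the score.
- *These are secondary measures.* True. The ATEC error rate is untouched, which limits the weight of the point without removing it.

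**Conclusion.** The point holds in a conditional form. It is certain that the SAP does not carry forward the protocol's GIH frequency score, omits four of ten items without a reason, and sets neither a single GI test nor a multiplicity rule.

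The size depends on three assumptions: separate tests, each at two-sided 0.05, and any one counting as a GI effect. Under these the chance of at least one false positive is at most about 26%. It is 21% at correlation 0.5 and about 11% at 0.9, against 5% for one score. In the direction of benefit it is about 14% if independent and 10% at correlation 0.5, against 2.5%. The correlation is assumed throughout.

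The SAP should be changed, because the first secondary objective currently has no defined test. The primary conclusion on ATEC does not depend on it.

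**What to change.** Before unblinding, amend SAP secondary measure 2 as follows.

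1. Name the GIH frequency score as the one GI secondary test, as Vivomixx minus placebo within child. The protocol's two contrasts with baseline reduce to this, since (active − baseline) − (placebo − baseline) = active − placebo.
2. Write the scoring rule, for example the sum of the 10 Likert items, and state the significance level.
3. Report the mean difference with a 95% confidence interval, and the proportion improved as the protocol promised.
4. Report individual symptoms descriptively, with estimates and 95% confidence intervals and no separate claims.

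If the six-symptom list is kept instead, give the reason for the four omissions and adjust across the six, for example by Holm's method.

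The documents do not say whether the blind has been broken. If it has, the scoring rule should be reported as chosen afterwards.

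The cost is SAP text and one scoring decision; all ten items are already in the questionnaire. The downsides are that a true effect on a single symptom carries less weight, and that a total mixes opposing symptoms such as constipation and diarrhoea.

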The correlations will be measured using Pearson's R unless the assumptions for Pearson's R are not met: if these are not met, then Spearman's Rho will be used. The relevant assumptions for Pearson's R are:

1. Absence of outliers: i.e. no outliers for each variable more than ± 3.29 Standard deviations from the mean.
2. Normality of variables: both variables will be assessed for normality using a Kolmogorov-Smirnov test.
3. Linearity: the relationship follows a straight-line relationship

¹ Note: assumption for paired-t-test is that the differences between the pairs are values are normally distributed, not that the values in each phase need to be normally distributed. The test does not assume homoscedasticity: i.e. that the standard deviations of the two groups are the same, so we will not test for this.

4. **Homoscedasticity:** how the datapoints are similarly distributed about a straight-line linear regression does not vary as either variables varies (technically the Standard error does not change significantly).

Assumptions three and four can be assessed visually using a scatter plot with a linear regression line added, and this can be generated by SPSS.

Secondary Analysis

Safety Analysis

The number of adverse events will be recorded that occurred to participants whilst on the active agent and placebo phases. The results will be presented both descriptively and assessed for a statistical difference in risk. To do this, the Relative Risk (RR) of adverse event as due to exposure to the active agent will be calculated with corresponding 95% confidence intervals.

Adherence and Deviation from Protocol Analysis

Similarly, adherence will be analysed descriptively for both the placebo and active agent phases, with totals for longer washout, withdrawal, lost to follow-up, did not reach full dose recorded for each phase. The total number of deviations will be summed for each phase, and the Relative Risk (RR) of deviation due to exposure to the active agent calculated with corresponding 95% confidence intervals.

Order of Treatment Effects

This analysis will replicate the between groups principal analysis; however, it will compare outcomes between the placebo/active and the active/placebo groups of participants rather than between the placebo arm and the active agent arm. Where dichotomous between groups data is considered, the Risk of exposure to the active agent in the first phase will be calculated with 95% confidence intervals.

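### The SAP names no paired method for yes/no outcomes measured on the same children in both phases; read in the usual way, the type-4 interval ignores the pairing and the adverse-event interval is not valid

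*SAP*

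**What the plan says.** The Protocol's section on baseline data and participant flow states the design logic: "As the study is a crossover study, each participant becomes their own control". Its Rationale for Trial Design gives reduced between-patient variability as the reason for choosing a crossover.

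The SAP, under Principal Analysis, follows that logic for interval outcomes. It uses a paired t-test, or a Wilcoxon signed-rank test if normality is rejected. Its footnote spells out the pairing: "assumption for paired-t-test is that the differences between the pairs are values are normally distributed".

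For yes/no outcomes the rule is different: "All between groups dichotomous data will be assessed for statistical significance by calculating the Relative Risk and corresponding 95% confidence intervals". The significance criterion is that "95% Confidence Intervals that do not contain the value 1 are statistically significant at" the 5% level. One listed secondary measure falls under this rule: "Bristol Stool Scale: proportion of phase participants with type 4 stool samples after active treatment".

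Two further SAP sections use the same summary. Under Safety Analysis, "The number of adverse events will be recorded that occurred to participants whilst on the active agent and placebo phases", and then "the Relative Risk (RR) of adverse event as due to exposure to the active agent will be calculated with corresponding 95% confidence intervals". Under Adherence and Deviation from Protocol Analysis, "The total number of deviations will be summed for each phase, and the Relative Risk (RR) of deviation due to exposure" to the active agent is computed.

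No variance formula is given for any of these intervals. No McNemar test, matched-pair relative risk, conditional or mixed logistic model, or GEE appears in either document.

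**The concern.** The textbook interval for a relative risk adds the variances of two independent proportions. Here the proportions on active and on placebo come largely from the same children, so their covariance belongs in the variance. Leaving it out discards the within-child information for which the crossover was chosen. Because the SAP ties significance to whether the interval excludes 1, a wrong width is also a wrong test.

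For type-4 stool, one result per child per phase, positive correlation makes the unpaired interval too wide, and a real difference is more easily missed.

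For adverse events and deviations the difficulty is more basic. The SAP counts events, and one child can contribute several. Neither the unit nor the denominator of the risk is defined, so an interval built for one yes/no result per child does not apply.

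**Working it through.** **The plan's own figure.** The documents give no power or precision figure for any yes/no outcome. The nearest is in the Protocol's Sample size calculation: 74 evaluable children, Wilcoxon signed-rank test, two-sided 5%, dz = 0.34, 80% power. A noncentral-t calculation with relative efficiency 3/π gives power 0.805 and a required n of 74. That figure reproduces, and it is a paired calculation.

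**Inputs for type 4.**
- n = 74 pairs, from the same section.
- Type-4 rates of p1 = 0.45 on active and p0 = 0.30 on placebo. These are assumed.
- Within-child correlation phi, varied from −0.2 to 0.5. The only within-subject correlation in the documents is 0.2, and it is stated for ATEC.

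**Formulas.**
- Unpaired: Var(log RR) = (1−p1)/(n·p1) + (1−p0)/(n·p0).
- Paired: Var(log RR) = (b+c)/(n1·n0), where b and c are the discordant counts and n1 and n0 the numbers positive on active and placebo.
- Expected concordant-positive share: p11 = p1·p0 + phi·√[p1(1−p1)p0(1−p0)]. Discordant share: p1 + p0 − 2·p11.

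**Numbers at phi = 0.2.**
- Unpaired: 0.55/33.3 + 0.70/22.2 = 0.0165 + 0.0315 = 0.0480, so SE = 0.219. With RR = 1.5 the 95% interval is 0.98 to 2.31.
- Paired: p11 = 0.135 + 0.2 × 0.228 = 0.1806. The discordant share is 0.75 − 0.3612 = 0.3888. The variance is 0.3888/(74 × 0.45 × 0.30) = 0.3888/9.99 = 0.0389, so SE = 0.197. The interval is 1.02 to 2.21.

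At these inputs the same data are non-significant by the unpaired interval and significant by the paired one.

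**Across phi.** SEs are closed form, as above. Power at 45% v 30% and null rejection at 35% in both phases come from multinomial simulation.

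| phi | SE unpaired | SE paired | Power unpaired v paired | Null rejection, unpaired |
|---|---|---|---|---|
| −0.2 | 0.219 | 0.239 | – | about 7.0% |
| 0 | 0.219 | 0.219 | agree | nominal |
| 0.2 | 0.219 | 0.197 | 46% v 54% | about 2.7% |
| 0.3 | 0.219 | 0.185 | 46% v 60% | 1.8% |
| 0.5 | 0.219 | 0.159 | 45% v 76% | 0.5% |

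As a further check with 30% in both phases, the nominal 95% unpaired interval covers 93.3% at phi −0.2, 95.5% at 0, 97.5% at 0.2 and 98.9% at 0.4. The paired interval covers about 95% throughout. With equal rates, the ratio of unpaired to paired SE is 1/√(1−phi), which at 0.2 is 1/√0.8 = 1.12.

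**Adverse-event counts.** Simulated with 74 children and no true difference, at an assumed mean of 0.4 or 0.8 events per child per phase, with and without clustering of events:
- Events divided by children, ordinary interval: coverage 75–88% at mean 0.4 and 45–61% at mean 0.8. At mean 0.8 the variance is undefined in 2–5% of runs.
- Poisson rate ratio: 95% without clustering of events within a child's phase, 82–89% with it.
- Any event per child, ordinary interval: 95–98%.

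The error can therefore go either way, depending on how the unit and denominator are read.

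**The case against.** The strongest reply is that the SAP never says the interval is unpaired. A matched-pair relative risk is also a relative risk with a 95% interval, so the text is compatible with a correct analysis. The between-groups label does not settle it, because the SAP puts the same label on ATEC and ABC and then analyses them with paired tests. This stands: a reader might infer that the SAP prescribes an independent-groups formula, and the documents do not say so. The wording does lean that way, since type 4 is defined as a per-phase proportion and deviations are totalled per phase before the ratio is taken. Two phase totals alone cannot give a paired interval. If a paired interval was intended, the SAP still needs to say so.

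A second reply is that the effect is modest and conservative at the one correlation the documents offer: an 8-point power loss at phi 0.2 under assumed rates. That also stands. The larger losses need correlations for which the documents give no support.

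Third, an unpaired relative risk is correct in one place. The SAP's Order of Treatment Effects section compares children randomised to different sequences. It is written to replicate the principal analysis, so a blanket switch to McNemar's test would carry a paired method into independent groups.

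**Conclusion.** The gap is real. For phase comparisons of yes/no outcomes the SAP names no paired method, and the default reading ignores the pairing.

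For type 4, the cost at 74 pairs and assumed rates of 45% v 30% runs from nothing at phi 0, through 8 percentage points of power at 0.2 and 14 at 0.3, to 31 at 0.5. At negative phi the unpaired interval is too narrow. Positive correlation in stool form is plausible, but it is an assumption.

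A reader might go on to infer that the adverse-event interval is also too wide and would hide a true excess. The documents do not support that. The SAP counts events, and repeat events in a child can make the interval too narrow, which risks a false signal instead. What can be said is that the interval is not valid as specified and its direction of error is unknown. The same holds for deviations.

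Only secondary, safety and adherence results are affected. The primary ATEC analysis is already paired. The change should be made, but it does not threaten the main conclusion.

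**What to change.** 1. Under Principal Analysis, replace the rule for yes/no outcomes compared between phases by McNemar's test, with a matched-pair relative risk (Var(log RR) = (b+c)/(n1·n0)) or paired risk difference and its 95% interval. Alternatively, use a GEE clustered on child with treatment and period terms, which keeps children who have data from one phase only.
2. State how children with one phase only are handled. McNemar's test and the matched-pair interval use complete pairs.
3. Under Safety Analysis and the deviation analysis, define the outcome as the child having at least one event (or deviation) in the phase and analyse it as in item 1. If counts are wanted, use a rate model clustered on child and state the denominator.
4. Under Order of Treatment Effects, state that yes/no outcomes are compared between the two sequence groups by an unpaired relative risk, so that the paired rule is not carried over.

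The cost is about one paragraph of SAP wording, with no new data as long as events and deviations are recorded by child and phase.

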# **Rationale for Trial Design**

A previous trial of VSL#3 probiotic (a formulation now known as Vivomixx) for children with IBS, showed it to be an effective treatment for relieving symptoms, severity and frequency of abdominal pain/discomfort and bloating/gassiness [53]. That trial used a randomised, placebo-controlled, double-blind crossover design and specifically excluded children with significant concomitant psychiatric or neurological illness, which would excludes those with diagnosed ASDs [18]. They adopted this study design because it offered the most stringent criteria for efficacy by minimising the variability between patients. This is particularly important in our study given the significant variability in GI and behavioural symptoms in those diagnosed with ASD and the varying levels of severity of these symptoms and is the reason we have chosen a randomised, placebo-controlled, double-blind crossover design. One potential drawback of the crossover design is the possibility of a "carryover" effect between treatments. To minimise this the IBS study used a 2-week washout period. Following advice from professor [name], the inventor of Vivomixx probiotic and asking the opinion of some parents of ASD children, we have designed the trial with a 4-week washout period. Other probiotic clinical trials have used washout periods varying from 3 weeks to 2 months [54], [55]. There may still be some carryover effect even after the 4-week washout but as we are not re-assessing until 16 weeks after the end of the first treatment phase, we do not consider that this will hamper results interpretation.

In setting the age range for the participants, we considered the fact that children in the UK are rarely formally diagnosed with ASD before age 3. Many of the patient referrals will come via Caudwell Children charity who support children with disabilities up to the age of 17 years so this influenced our upper cut off age. The other factor we considered was the evidence that the gut microbiome matures by the age of 3 years and then remains largely the same until old age. Keeping the age range as wide as possible means that if the treatment proves successful, the recommendations for treatment will apply to a wide group.

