The principal analysis of the primary outcome measure will be performed on the Placebo-first group vs Placebo-second group, and between the Active-first group vs the Active-second group to assess for an order effect.

Order of Treatment group demographics

The demographics of the placebo/active and the active/placebo groups of participants, will be analysed and compared for significant differences. The characteristics that will be analysed are age, gender, baseline ATEC total score and additional diagnoses.

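### The SAP's order-of-treatment check reuses paired tests on groups made up of different children and names no unpaired test for interval outcomes

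*SAP*

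**What the plan says.** The SAP's Principal Analysis compares active and placebo phases "assuming no order of treatment effects, which will be investigated in the secondary analysis". It sets one route for interval outcomes: "All between groups interval data will be subject to the following protocol for statistical analysis". The steps are:

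- summaries for each phase;
- a "Kolmogorov-Smirnov test to assess normality in the between phase differences";
- a paired t-test, or a Wilcoxon signed-rank test if normality is rejected.

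A footnote confirms that the "assumption for paired-t-test is that the differences between the pairs" are what must be normal.

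The section on Order of Treatment Effects then states: "This analysis will replicate the between groups principal analysis; however, it will compare outcomes between the placebo/active and the active/placebo groups of participants". For binary outcomes it writes a separate rule, which includes an interval estimate: "Where dichotomous between groups data is considered, the Risk of exposure to the active agent in the first phase will be calculated". For the primary outcome it adds: "The principal analysis of the primary outcome measure will be performed on the Placebo-first group vs Placebo-second group", and likewise Active-first against Active-second.

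On carryover, the protocol's Rationale for Trial Design says: "There may still be some carryover effect even after the 4-week washout". The same sentence goes on to judge that this will not hamper interpretation, because the next assessment comes 16 weeks after the first treatment phase ends.

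**The concern.** A paired test needs two values from the same child. Placebo-first and Active-second are the placebo/active children; Active-first and Placebo-second are the active/placebo children. Every order comparison therefore has different children on its two sides. The binary rule was adapted to this and the interval rule was not, and the SAP names no independent-samples test anywhere.

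At stake is the check on the assumption under which the primary result is read. The analyst must either invent pairs or use a test that the SAP does not name. A first-period active v placebo estimate, which carryover cannot reach, is not explicitly specified either. The comparison of sequence groups does not say which period it concerns. The protocol's mixed model with group and time could yield such an estimate, but the SAP does not take that model up.

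**Working it through.** **1. Which contrasts have pairs.** Let τ be the treatment effect, π the period effect and λ the carryover from active into the following placebo period. Assume no carryover from placebo. Cell means, relative to Placebo-first:

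| Sequence | Period 1 | Period 2 |
|---|---|---|
| Active/placebo | τ | π + λ |
| Placebo/active | 0 | π + τ |

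- Placebo-second minus Placebo-first = π + λ. Different children, so there are no pairs and no differences for the normality test.
- Active-second minus Active-first = π. The same holds.
- Active/placebo v placebo/active: each child who completes both phases has an active-minus-placebo difference, so the normality step can be run. Its expectation is τ − π − λ in one sequence and τ + π in the other. Comparing the two sets needs an unpaired test.
- Within-child sums: the contrast between sequences is (τ + π + λ) − (π + τ) = λ. This equals the first bullet minus the second, so it uses contrasts already planned and removes the period effect.

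**2. The plan's own figure, and the SDs it implies.** Protocol, Sample size calculation: 74 children, signed-rank test, two-sided 5%, dz 0.34, 80% power. With effective n = 74 × 3/π = 70.7 (here π is the constant 3.14) and noncentrality 0.34 × √70.7 = 2.86, power is 80.5%, so the figure reproduces. No SD is given. The implied values are 15/0.50 = 30, 15/(0.34 × √(2 × 0.8)) = 34.9 and 15/0.37 = 40.5, all treated as assumptions.

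**3. Unequal groups.** Assume 41 children per sequence and 8 of 82 lost at random (the protocol's 10%, leaving 74). P(equal) = C(41,4)²/C(82,8) = 0.288, so P(unequal) = 71%. The mean size difference is 2.1 children, and it is 4 or more in 26% of trials.

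**4. One arbitrary pairing.** Simulated normal data, 37 v 37, SD 34.9. The paired t-test under one random order disagrees with Welch's test at 0.05 in about 2%, 2%, 3% and 5% of datasets at gaps of 0, 3.75, 7.5 and 15 points. Average rejection rates barely differ: about 5% for both with no gap, and 43 to 45% at 15 points.

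**5. What undetected carryover would do (illustration).** With balanced sequences the pooled estimate is [(τ − π − λ) + (τ + π)]/2 = τ − λ/2. For τ = 15 and λ = 7.5 it is 11.25. Replacing dz by 0.34 × (1 − 0.5/2), power falls from 80% to 56%.

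**6. What a valid check could detect.** Sums of two change scores share one baseline, so their variance is SD² × [2(1 + ρ) + 4 − 8r]. Here ρ is the correlation between phases and r that with baseline. With 37 per group, ρ = 0.2 and complete carryover of 15 points:

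- SD 40.5, r 0.2: factor 4.8, d = 15/(40.5 × √4.8) = 0.17, power 11%.
- SD 30, r 0.7: factor 0.8, d = 15/(30 × √0.8) = 0.56, power 66%.

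At half carryover the range is 6 to 22%. With ρ equal to r it is 6 to 12% (half) and 11 to 35% (complete). The 66% corner implies a correlation of (0.2 − 0.49)/0.51 = −0.57 between the two post-treatment scores at a given baseline, which is implausible.

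**7. First-period estimate.** Baseline-adjusted, d = 15/(SD × √(1 − r²)), 37 per group, 71 df. At SD 34.9 power is 46% (r 0.2) to 72% (r 0.7), against 80% for the crossover at ρ = 0.2. The 95% CI half-width is 11.6 to 15.9 points, against 10.2.

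**The case against.** The best defence is that this is one unnamed test in a secondary analysis. The SAP signals that the comparison changes, a competent analyst would use an ordinary unpaired test, and the summaries in the first step, repeated by sequence, would let a reader form a rough unadjusted first-period contrast. The protocol also allows the analysis plan to be updated at blind review and finalised before unblinding. Most of this stands and limits the harm. It does not supply the missing rule: the paired route is the only one written for interval data, although the binary rule was adapted.

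Four stronger readings are tempting, and the documents do not support them.

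- That the order check cannot be done at all. The data support it; only the test is missing.
- That the verdict is largely a matter of row order. Over 200 random orders, at least one crosses 0.05 against the others in 12 to 35% of datasets, but that counts any of 200 tries. An analyst uses one order, so the disagreement rates in step 4 apply.
- That the test would be chosen with knowledge of the allocation. Nothing shows this.
- That carryover is present or the primary result invalid. The protocol concedes only a possibility and argues that the late second assessment limits it. That argument is reasonable but untested, which is why the check should work.

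**Conclusion.** The stated rule is wrong as written for interval outcomes, including the primary. The two same-treatment contrasts contain no pairs. The sequence-group comparison has within-child differences but needs an unpaired test, which the SAP does not name. The binary order analysis is workable. This conclusion rests on the SAP's text alone.

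The size of the problem is modest. Literal use either fails on unequal groups or gives a slightly arbitrary answer without inflated error, and the primary estimate and p-value do not change. The percentages depend on random loss, normal data and SDs inferred from effect sizes in the protocol that do not agree with one another; the correlations and carryover fractions are assumptions. Under most of them even a valid carryover test has low power, so a non-significant order check should not be read as showing that carryover is absent.

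**What to change.** In the SAP's Order of Treatment Effects section, for interval outcomes:

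1. Replace the instruction to replicate the principal analysis with independent-sample tests (Welch, or rank-sum) between the two sequences: on within-child active-minus-placebo differences for the period effect, and on within-child sums for carryover. One mixed model with treatment, period and sequence would serve instead.
2. State that in a two-period crossover the sums contrast cannot separate carryover from sequence-group differences or treatment-by-period interaction, and that its power is low under most assumptions.
3. Report, always and not triggered by a pre-test, a first-period ANCOVA of Visit 3 ATEC on group and baseline ATEC, with a 95% CI, as a sensitivity estimate.

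The cost is SAP wording and one extra regression. Visit 3 ATEC is already collected before the second treatment period, so no new visit is needed. The downside is that the first-period estimate is less precise than the crossover estimate, so it supports the primary result and does not replace it.
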